# 8.4.2 Electrocardiogram (ECG)

ECGs must be recorded according to the ECG investigator manual. The preferred sequence of cardiovascular data collection during study visits is ECG collection first, followed by vital signs, and blood sampling. The Fridericia QT correction formula (QTcF) should be used for clinical decisions.

Triplicate 12-lead ECGs are to be collected approximately 2 minutes apart for central analysis. The mean QTcF value for each visit will be calculated from the triplicate ECGs for each participant. At Weeks 2, 12 and 52 pre and post-dose assessments should be collected (refer to Table 8-1), post dose assessment should be measured

and the mean QTcF

value for each timepoint will be calculated from the triplicate ECGs for each participant.

All ECGs, including unscheduled safety ECGs with clinically relevant findings collected during the study needs to be transmitted to the central ECG laboratory for review.

A monitoring or review process should be in place for clinically significant ECG findings throughout the study and especially at baseline before administration of study treatment.

In the event that a clinically significant ECG abnormality is identified at the site (e.g., severe arrhythmia, conduction abnormality of QTcF > 450 ms (males)/ 460 ms (females)), a copy of the assessment is sent to the core laboratory for expedited review if applicable, and the ECG is repeated to confirm the diagnosis. If the participant is hemodynamically compromised, the investigator or a medically qualified person must initiate appropriate safety procedures without delay (for example cardioversion).

Additional, unscheduled, safety ECGs may be repeated at the discretion of the investigator at any time during the study as clinically indicated. For any ECGs with participant safety concerns, two additional ECGs must be performed to confirm the safety finding.

Clinically significant abnormalities must be recorded on the CRF as either medical history/current medical conditions or adverse events as appropriate.

If participants cannot visit the site for protocol specified safety ECG assessments (per Section 4.6), an alternative machine (local) may be used.

# 8.4.3 Pregnancy and assessments of fertility

All pre-menopausal women who are not surgically sterile will have pregnancy testing at screening (serum), at baseline (Day 1, before administration of study medication (urine)), and every 4 weeks thereafter (urine). Where the visit interval is greater than 4 weeks, or in the case that the participants cannot visit the site, the participants will be provided with urine pregnancy tests kits to be used at home. Results must be provided to the investigator at the next scheduled visit. Participants should be instructed to perform the urine pregnancy test first and only if the test result is negative proceed with the administration of the study treatment.

A positive urine pregnancy test needs to be confirmed with a serum test. Where a home urine pregnancy test is positive the participant must contact the investigator and return to site for a serum pregnancy test, in the case that participants cannot visit the site an alternative (local lab) can be used. If positive the participant must be discontinued from study treatment.

A communication process should be established with the participant so that the site is informed and can verify the pregnancy test results (e.g., following country-specific measures).

Additional pregnancy testing might be performed if requested by local requirements.

# **Assessments of fertility**

Medical documentation of oophorectomy, hysterectomy, or bilateral tubal ligation must be retained as source documents. Subsequent hormone level assessment to confirm the woman is not of child-bearing potential must also be available as source documentation in the following cases:

- 1. Surgical bilateral oophorectomy without a hysterectomy
- 2. Reported 12 months of natural (spontaneous) amenorrhea with an appropriate clinical profile.

In the absence of the above medical documentation, FSH testing is required of any female participant regardless of reported reproductive/menopausal status at screening/baseline.

### 8.4.4 Appropriateness of safety measurements

The selected safety monitoring assessments (including laboratory assessments covering clinical chemistry, hematology, coagulation status as well as clinical and physical assessments, triplicate ECG monitoring and general AE assessments) are reliable and well-established standard measures which allow valid and close safety monitoring of the trial's patient population, with regards to their disease, to the compound they are treated with, remibrutinib, and also to their overall medical safety.

### 8.5 Additional assessments

[figure not shown]
# 8.5.1 Clinical Outcome Assessments (COAs)

### **Trial Feedback Questionnaire**

This study includes an optional anonymized questionnaire, the 'Trial Feedback Questionnaire' for trial participants to provide feedback on their clinical trial experience at 3 timepoints at the start, during and at the end of the trial. Individual trial participant responses will not be reviewed by investigators. Responses may be used by the sponsor to understand where improvements can be made in the clinical trial process. This questionnaire does not ask questions about the trial participant's disease, symptoms, treatment effect or adverse events and therefore is not considered as trial data

In the case that participants cannot come to site (see Section 4.6), these questionnaires would be available on their electronic device.

# 9 Discontinuation and completion

# 9.1 Discontinuation from study treatment and from study

# 9.1.1 Discontinuation from study treatment

Discontinuation of study treatment for a participant occurs when study treatment is permanently stopped for any reason (prior to the protocol planned completion of study drug administration) and can be initiated by either the participant or the investigator.

The investigator must discontinue study treatment for a given participant if, he/she believes that continuation would negatively impact the participant's well-being.

Discontinuation from study treatment is required under the following circumstances:

- Participant decision (request in writing or verbally)
- Pregnancy
- Use of prohibited treatment requiring study treatment discontinuation as detailed in Table 6-2 or discontinuation of highly effective methods of contraception as detailed in Section 5.2
- Any situation in which continued study participation might result in a safety risk to the participant

- Emergence of the following AEs:
  - any adverse events that in the judgement of investigator, taking into consideration the participant's overall status, prevents the participant from continuing participation in the study, including:
    - hypersensitivity reactions,
    - severe/serious infections
    - clinically significant spontaneous bleeding events
    - new confirmed diagnosis of malignancy of any organ system (other than localized basal cell carcinoma of the skin or in situ cervical cancer)
  - Platelets < 75 000/mm3
  - Abnormal renal laboratory results requiring discontinuation (see Section 16.3)
  - Abnormal liver laboratory results requiring discontinuation (see Section 16.2)
  - Any other laboratory abnormalities that in the judgment of the investigator, taking into consideration the participant's overall status, prevents the participant from continuing participation in the study
  - Participant received a live virus vaccination during the study

If discontinuation from study treatment occurs, the investigator should make a reasonable effort to understand the primary reason for the participant's discontinuation from study treatment and record this information.

# All participants who discontinue from study treatment prematurely should complete the Early treatment discontinuation visit at the time of treatment discontinuation.

For participants who discontinue from study treatment prior to Week 12, where possible they should be requested to return for visits after the Early treatment discontinuation visit as per the Assessment Schedule (Table 8-1) up to and including the Week 12 timepoint. At the Week 12 timepoint the study discontinuation visit should be performed

If the participant declines to continue with assessments as per the visit schedule up to Week 12, then they should complete the safety follow-up visit after the Early treatment discontinuation visit.

Participants who discontinue from study treatment after Week 12 should complete the safety follow-up visit indicated in the Assessment Schedule (Table 8-1) whenever possible.

If the participant cannot or is unwilling to attend any visit(s), the site staff should maintain regular telephone contact with the participant, or with a person pre-designated by the participant. This telephone contact should preferably be done according to the study visit schedule.

After discontinuation from study treatment, at a minimum, in abbreviated visits, the following data should be collected at clinic visits or via telephone/email contact:

- New / concomitant treatments
- Adverse Events / Serious Adverse Events

The investigator must also contact the IRT to register the participant's discontinuation from study treatment.

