#### 4 Rationale

### 4.1 Rationale for study design

The primary analysis of the Phase 2b dose-range finding study CLOU064A2201 demonstrated that treatment with remibrutinib 25 mg b.i.d. substantially improves signs and symptoms of CSU compared to placebo, in participants who have not adequately responded to prior treatment with H1-antihistamines and other CSU therapies including omalizumab. This Phase 3 study is designed to evaluate the safety, tolerability and efficacy of remibrutinib at a dose of 25 mg b.i.d. (as determined by the Phase 2b dose-range finding study CLOU064A2201, see also Section 4.2) in adult CSU patients. It is an open-label, single arm study that consists of three phases:

- 1. **Screening period**: the screening period of up to four weeks will allow the assessment of eligibility of participants and the determination of baseline disease activity.
- 2. Open-label treatment period: during this treatment period of 52 weeks, an open-label design without a comparator arm is considered adequate to evaluate long-term safety for CSU in Japanese participants and accepted by Japanese Health Authority. The treatment period will provide long-term safety and efficacy data to characterize the value of remibrutinib in CSU.
- 3. **Follow-up period**: a treatment-free follow-up period of four weeks at the end of the study will be implemented for all participants who do not enroll into the extension study (currently being considered). This allows the assessment of safety after treatment discontinuation as well as the dynamics of potential re-occurrence of CSU signs and symptoms after treatment discontinuation.

The study population consists of participants with CSU (UAS7 score  $\geq$  16, with HSS7 score  $\geq$  6 and ISS7 score  $\geq$  6), who have a duration of CSU of  $\geq$ 6 months and who are inadequately controlled despite treatment with second generation H1-antihistamines at least at locally label approved dose. Importantly, patients who have inadequately responded to or did not tolerate anti-IgE biologic treatments are also eligible for this study. Thus, CSU patients with high unmet medical need are the target population for this study.

The primary endpoint of this study is overall safety, assessed as treatment-emergent adverse events during the study, as the number of Japanese CSU patients exposed to remibrutinib at the intended or higher dose in the global studies (CLOU064A2201, CLOU064A2201E1 and

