**Discontinuation from study** 

### Amended Protocol Version No. 01 (Clean)

Discontinuation from study is when the participant permanently stops receiving the study treatment, and further protocol-required assessments or follow-up, for any reason, including participant's decision (requested in writing or verbally).

If the participant agrees, a final evaluation at the time of the participant's study discontinuation should be made as detailed in the assessment table (refer to Section 8).

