- Drug interrupted/permanently discontinued
- 6. Its outcome

Conditions that were already present at the time of informed consent should be recorded in medical history of the participant.

Adverse events (including lab abnormalities that constitute AEs) should be described using a diagnosis whenever possible, rather than individual underlying signs and symptoms.

Adverse event monitoring should be continued for at least 30 days following the last dose of study treatment.

Once an adverse event is detected, it must be followed until its resolution or until it is judged to be permanent (e.g., continuing at the end of the study), and assessment must be made at each visit (or more frequently, if necessary) of any changes in severity, the suspected relationship to the interventions required to treat it, and the outcome.

Information about adverse drug reactions for the investigational drug can be found in the IB.

Abnormal laboratory values or test results constitute adverse events only if they fulfill at least one of the following criteria:

- they induce clinical signs or symptoms
- they are considered clinically significant
- they require therapy

Clinically significant abnormal laboratory values or test results must be identified through a review of values outside of normal ranges/clinically notable ranges, significant changes from baseline or the previous visit, or values which are considered to be non-typical in participant with the underlying disease. See Section 16.1, Section 16.2 and Section 16.3 for alert ranges for laboratory and other test abnormalities.

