2.1.1.3 On-treatment period for safety assessment

The on-treatment period is defined as the period from the first date of dose intake of treatment to the last date of dose intake + a period of time accounting for remaining exposure to drug in relation to the potential pharmacodynamic effects of remibrutinib. It is the reference period for safety analyses on adverse events, laboratory, vital signs, etc.

Remibrutinib has a short half-life (5hrs). Due to the covalent-binding mode, pharmacodynamic effects, including target inhibition in tissues and cells is to be taken into account for determining the follow-up time after the last study drug dose, which is beyond 5 half-lives'. As a conservative measure, 28 days was selected.

The on-treatment period lasts from the date of first administration of study treatment to 28 days after the date of the last actual administration of the study treatment or the end of study where the end of study is either of the date of study discontinuation, or study completion, or safety follow-up completion or cut-off date, depending on participant's status.

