If a participant visited the site earlier than scheduled visit day, e.g., Week 4 on Day 25 and ETD visit on Day 29, ETD visit will be remapped to Week 4. As the participant already performed Week 4 scheduled visit, the remapped Week 4 (ETD visit) will not be used.

If a participant visited the site late than scheduled visit day, e.g., Week 4 on Day 25, ETD visit on Day 58 and SD visit on Day 85, both ETD visit and SD visit will be remapped to Week 12. In this case, ETD visit will be used as Week 12, and Week 8 will be missing.

| Assessment visit | Scheduled visit Day | Assessment window |
|------------------|------------------------|--------------------|
| Week 2 | 15 | Day 2 to Day 15 |
| Week 4 | 29 | Day 16 to Day 29 |
| Week 8 | 57 | Day 30 to Day 57 |
| Week 12 | 85 | Day 58 to Day 85 |
| Week 16 | 113 | Day 86 to Day 113 |
| Week 20 | 141 | Day 114 to Day 141 |
| Week 24 | 169 | Day 142 to Day 169 |
| Week 32 | 225 | Day 170 to Day 225 |
| Week 40 | 281 | Day 226 to Day 281 |
| Week 52 | 365 | Day 282 to Day 365 |

Table 2-4Assessment window for vital signs, clinical chemistry, hematology,
urinalysis until Week 52

For the assessments which are not collected at every visit (e.g., DLQI etc.), assessment window will be combined. For example, DLQI is collected at Week 4, Week 12, Week 24 and Week 52. The assessment window will be combined as Table 2-5.

Table 2-5Assessment window for DLQI until Week 52

| Assessment visit | Scheduled visit day | Assessment window |
|------------------|------------------------|-------------------|
| Week 4 | 29 | Day 2 to Day 29 |

| Week 12 | 85 | Day 30 to Day 85 |
|---------|-----|--------------------|
| Week 24 | 169 | Day 86 to Day 169 |
| Week 52 | 365 | Day 170 to Day 365 |

Table 2-6 show the assessment windows of days for each assessment.

| | | | | - | | | | | | |
|---|--------|--------|--------|---------|---------|-------------|-------------|---------------------|-------------|-------------|
| Assessment visit | Week 2 | Week 4 | Week 8 | Week 12 | Week 16 | Week 20 | Week 24 | Week 32 | Week 40 | Week 52 |
| Scheduled visit day | 15 | 29 | 57 | 85 | 113 | 141 | 169 | 225 | 281 | 365 |
| Vital signs Clinical chemistry Hematology Urinalysis | 2-15 | 16-29 | 30-57 | 58-85 | 86-113 | 114- 141 | 142- 169 | 170- 225 | 226- 281 | 282- 365 |
| Coagulation Panel | 2-29 | | 30-85 | | 86-169 | | | 170-28 ⁻ | 1 | 282- 365 |
| | | | | | | | | | | |
| | | | | | | | | | | |

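### Protocol 9.1.1 names no safety follow-up visit for participants who stop treatment before Week 12 and keep attending, so scheduled observation can end inside the 28-day and 30-day post-dose windows

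*Protocol*

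**What the plan says.** Protocol Section 9.1.1 sets three routes after early discontinuation of study treatment, each starting with the early treatment discontinuation (ETD) visit.

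- **Stops before Week 12, keeps attending.** Returns for scheduled visits up to Week 12. Then: "At the Week 12 timepoint the study discontinuation visit should be performed". No later visit is named.
- **Stops before Week 12, declines visits.** For this group, "then they should complete the safety follow-up visit after the Early treatment discontinuation visit".
- **Stops after Week 12.** "Participants who discontinue from study treatment after Week 12 should complete the safety follow-up visit indicated in the Assessment Schedule", whenever possible.

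Section 9.1.2 gives study discontinuation a final meaning: "Discontinuation from study is when the participant permanently stops receiving the study treatment, and further protocol-required assessments or follow-up, for any reason". The glossary agrees. Table 8-1 keeps two separate columns: Week 52/study discontinuation, and Week 56/safety follow-up/study completion.

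Three other places set the length of follow-up. Section 4.1 says the four-week treatment-free period "will be implemented for all participants who do not enroll into the extension study". Section 10.1.1 says: "Adverse event monitoring should be continued for at least 30 days following the last dose of study treatment". Section 12.4.1 runs the on-treatment period of the primary endpoint to 28 days after the last dose. SAP 2.1.1.3 keeps the 28 days but adds the end of study as an alternative limit, where "the end of study is either of the date of study discontinuation, or study completion, or safety follow-up completion or cut-off date", depending on the participant's status.

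**The concern.** The visit is named in two of the three routes and absent from the third. A site that follows 9.1.1 as written would close a cooperative participant's study at Day 85 even if the last dose was only days before. If the other two groups are seen about four weeks after the last dose, as 4.1 implies, the cooperative participant has less scheduled safety follow-up than one who declines visits. No passage gives a reason for that.

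Safety is the primary objective, and the summary measure is the proportion of participants with at least one treatment-emergent adverse event. For a given participant, a shorter window can remove events from that count but cannot add any. The reasons for stopping listed in 9.1.1 include infection, bleeding, low platelets, and liver or renal laboratory abnormalities, where a later laboratory result is informative.

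The SAP clause adds a second route to the same problem. Suppose an event is reported by telephone after Day 85 but within 28 days of the last dose. If the Week 12 study discontinuation date is taken as the end of study, that event would fall outside the on-treatment period.

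**Working it through.** **Inputs**

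- Week 12 visit: Day 85 (Table 8-1; SAP Table 2-4, row "Week 12 | 85 | Day 58 to Day 85"). Check: 7 × 12 + 1 = 85, as stated. Day 58 in that row is the start of a visit-mapping window and plays no part below.
- Primary endpoint window: 28 days after the last dose (12.4.1, SAP 2.1.1.3).
- AE monitoring: at least 30 days after the last dose (10.1.1). SAE collection: 30 days (10.1.3).
- About 70 treated participants and about 15% dropout (12.8).

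**Step 1: which last-dose days are affected.** Let d be the day of the last dose. With exit at Day 85, observed days = 85 − d.

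- The 28-day window is short when d + 28 > 85, so d ≥ 58. Days 58-84 (27 days) leave 27 down to 1 day.
- The 30-day period is short when d + 30 > 85, so d ≥ 56. Days 56-84 (29 days) leave 29 down to 1 day.

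| Last dose (day) | Days observed to Day 85 | Short of 28 | Short of 30 |
|---|---|---|---|
| 55 | 30 | 0 | 0 |
| 56 | 29 | 0 | 1 |
| 58 | 27 | 1 | 3 |
| 71 | 14 | 14 | 16 |
| 78 | 7 | 21 | 23 |
| 84 | 1 | 27 | 29 |

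Anyone whose last dose was on or before Day 55 is fully covered by the Week 12 visit.

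**Step 2: how many participants.** Expected dropouts: 0.15 × 70 = 10.5. The documents do not give the timing of dropout, so three assumptions are shown. Each takes stops as evenly spread within the first 84 days and assumes that all early stoppers attend to Week 12.

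| Assumed timing | Stops before Week 12 | In 28-day gap (× 27/84) | In 30-day gap (× 29/84) |
|---|---|---|---|
| Even over 364 days | 10.5 × 84/364 = 2.42 | 0.78 | 0.84 |
| Half before Week 12 | 5.25 | 1.69 | 1.81 |
| All before Week 12 | 10.5 | 3.38 | 3.63 |

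**Step 3: does the SAP restore the window?** Section 12.4.1 has no end-of-study clause. SAP 2.1.1.3 has one, and study discontinuation is among the dates it lists. For a last dose on Day 71, 28 days runs to Day 99. If the Week 12 study discontinuation date counts as the end of study, the SAP window closes at Day 85, which is 14 days earlier.

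**The case against.** The best counter-argument is that 9.1.1 is silent and that other text fills the silence.

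- Section 9.4, on early termination by the sponsor, treats participants as having discontinued study treatment and has sites schedule both the study discontinuation and the study completion visits, as appropriate. In Table 8-1 study completion is the safety follow-up column. So the study discontinuation visit need not be the last contact.
- Section 4.1 promises follow-up to everyone who does not enter the extension. Sections 2.1 and 12.4.3 say data collection continues in the follow-up period after discontinuation. SAP 2.5.3 promises every effort to follow such participants to study end.
- The 30-day AE and SAE duties do not stop at Week 12. Section 9.1.1 allows AE collection by telephone or email after treatment discontinuation and gives no end date for it.
- Affected participants already have laboratory tests, ECG and vital signs at the ETD visit and again at Week 12.
- The study is descriptive with no hypothesis test, and anyone with an earlier treatment-emergent event is already counted.

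Much of this stands. A reader might infer that these participants leave with no safety follow-up, or that adverse events will be lost from the primary endpoint. The documents support neither as fact, because the reporting duties bind and 9.4 allows a later visit. A reader might also take the SAP remapping example (ETD visit on Day 58, study discontinuation visit on Day 85) as a 27-day follow-up. That example illustrates visit mapping and gives no last-dose date, so it shows nothing about post-dose observation. Nor do the documents give any figure showing that the affected stops would be mainly adverse-event driven.

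What the counter-argument does not remove is the text itself. The other two routes name the visit and this one does not, 9.1.2 defines study discontinuation as the end of follow-up, and telephone contact provides no laboratory test, ECG or vital signs.

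**Conclusion.** The inconsistency is real. On a literal reading, participants who stop before Week 12 and keep attending have 1-27 days of scheduled observation when the last dose falls on Days 58-84, against the 28-day primary endpoint window. They have 1-29 days when it falls on Days 56-84, against the 30-day monitoring period. This conflicts with Sections 4.1, 10.1.1 and 12.4.1, and Section 9.4 points the other way.

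The exposure is one scheduled visit with its assessments, together with a possible early close of the SAP on-treatment window. Loss of adverse event data is possible but not shown.

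About 1-2 of 70 participants are affected if dropout is even over the year or half of it precedes Week 12, and up to about 4 if all of it does. These counts rest on the assumed timing and on full attendance to Week 12. The window arithmetic rests only on the Day 85 visit and a literal reading of 9.1.1. The point deserves correction because it bears on the primary safety endpoint, but it does not threaten the trial's conclusions.

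**What to change.** Reconcile Section 9.1.1 with 4.1, 9.4, 10.1.1, 10.1.3 and 12.4.1 and with SAP 2.1.1.3, on two points.

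1. Section 9.1.1 should state whether the existing Table 8-1 safety follow-up visit also applies to participants who stopped before Week 12 and kept attending, when the Week 12 visit falls inside the protocol's own post-dose window, as it does for the other two groups.
2. SAP 2.1.1.3 should make clear that the Week 12 study discontinuation date does not cut the 28-day on-treatment window for these participants, so that events reported within 28 days of the last dose are counted.

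If the protocol can no longer be changed, the study report can give the number of participants observed for fewer than 28 days after the last dose.

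The cost is about one sentence in the protocol and one clause in the SAP. If the visit is found to apply, it adds at most one already-defined visit per affected participant. No sample size figure changes.
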